Patient is without a three-month or 12-month clinical follow-up, or has follow-up appointments that are not at 3 or 12 months	
The RA will either call patient to come in for a follow-up to complete the follow-up data collection. If participant cannot meet with the RA, a questionnaire package will be mailed for the participant to complete. The date that the patient returns their questionnaire as the final appointment date; however, the research associate should note that it is the follow-up date not the final appointment date; however, the RA should note that it is the follow-up date not the final appointment date. Download data will be obtained through the participants PAP provider.
 
The RA will give the patient a pre-paid parking voucher for all appointments that are outside of standard clinical visits

Patient is discharged by the clinic	The RA will approach the patient to continue the study.
Patient withdraws from the study after being discharged by the ACP/Provider	
The RA will ask permission to collect their data on healthcare utilization and visits to the sleep centre.
 
If participant declines, the RA will cease ongoing data collection. Data collected up to the point of participant withdrawal will be retained.

Cannot contact patient (i.e. called once a week for a month)	The RA will send a participation letter to the patient requesting that they contact the RA to coordinate a time to complete the questionnaires and HSATs. If the RA does not hear from the patient, they will be considered lost to follow-up.
Patient does not bring their PAP machine to the appointment	The patient will be called to bring the machine in to be downloaded by a therapist. If they are unable to make it in to the FMC Sleep Centre, a download compliance form will be faxed to the provider requesting the needed information be sent to the FMC Sleep Centre addressed to the booking clerk. The RA will provide the booking clerk with a list of all requested downloads and HSATs which she will flag and provide to the RA.

DATA COLLECTION

SUMMARY SHEET

	Data to collect	Data source	Photocopy, handwritten or original copy
Recruitment	Study consent	From patient during HSAT appointment	Original copy
	Triage Criteria (Level 3 HSAT or ANC)	Level 3 HSAT – patient's chart, if any. ANC – Patient Questionnaire.	Handwritten
	HSAT – RDI, Mean O2 saturation, mean O2 saturation, time under 90%	HSAT Summary page, day after patient completes HSAT.	Photocopy

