Evaluation of a “Fast Track” Respiratory Therapy Clinic for Patients with Suspected Severe Sleep-Disordered Breathing

STATISTICAL ANALYSIS PLAN

NCT#: 02191085

Document Date: February 16, 2017

Evaluation of a "Fast Track" Respiratory Therapy Clinic for Patients With Suspected Severe Sleep-Disordered Breathing

Statistical Analysis

This study will use a modified intention to treat analysis, in which results will be analyzed for patients who are randomized and have treatment adherence data three months after initiating PAP therapy.

Paired t tests will be used to compare clinical outcomes from baseline to 3 months and one year and unpaired t tests will be used to compare time to treatment initiation and measures of patient demand. Multiple logistic regression will be used to identify predictors of study outcomes using variables identified as predictive on univariate regression. Outcomes will be transformed into binary variables based on clinically relevant cut-offs.

The economic analysis will be performed using the perspective of a publicly funded healthcare system. An estimate of mean utility scores based on the HUI questionnaire will be calculated and the average quality-adjusted life- year (QALY) will be calculated for each study arm. Using bootstrapping, we will compare the difference in mean costs and QALYs between the study arms to generate an incremental cost-effectiveness ratio for an ACP-led clinic compared to traditional physician-led care. Sensitivity analyses will be performed to evaluate the effect of changes in physician fees, RT salaries, diagnostic testing costs and treatment costs.

All study outcomes will be analyzed in different subgroups to clarify the impact of ACP-led care for patients with different patient flow pathways or clinical treatments. Pre-specified subgroups include:

- Patients who undergo PSG vs. patients who do not undergo PSG
- Patients treated with bilevel PAP vs. patients treated with CPAP
- Patients who are treated with oxygen vs. patients treated without oxygen

Sample Size

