The study is powered to assess the non-inferiority of ACP-led care compared to usual care by sleep physicians. A non-inferiority margin of -1 hour of PAP adherence was determined by consensus of the investigators and has been used in previous studies comparing different models of care for SDB. One hundred thirty eight patients (69 in each arm) will be required to achieve 90% power with a type I error of 0.05, using this non-inferiority margin and a standard deviation of 2 hours of nightly CPAP use. The standard deviation used in the sample size calculation was based upon the results of two previous studies. To account for withdrawals and loss to follow-up (approximately 15% at the FMC Sleep Centre), recruitment will continue until three-month adherence data is available for 150 patients.

Reference: Ip-Buting A, Kelly J, Santana MJ, Penz ED, Flemons WW, Tsai WH, et al.

Evaluation of an alternative care provider clinic for severe sleep-disordered breathing: a study protocol for a randomised controlled trial. *BMJ Open*. 2017 Mar;7(3):e014012.

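### The SAP names no between-arm analysis for three-month PAP hours, its powered endpoint, and pre-specifies no adjustment for the HSAT severity measures taken before randomisation

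*SAP*

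**What the plan says.** **The powered endpoint.** The SAP's Sample Size section rests on nightly PAP use: "A non-inferiority margin of -1 hour of PAP adherence was determined by consensus of the investigators". The calculation uses "a standard deviation of 2 hours of nightly CPAP use", and the resulting number "will be required to achieve 90% power with a type I error of 0.05". Whether 0.05 is one-sided or two-sided is not stated. For the final count, "recruitment will continue until three-month adherence data is available for 150 patients".

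**The analyses named.** The SAP's Statistical Analysis section gives four:
- Paired t tests for change in clinical outcomes from baseline.
- Between arms: "unpaired t tests will be used to compare time to treatment initiation and measures of patient demand".
- Multiple logistic regression on dichotomised outcomes to "identify predictors of study outcomes", with variables chosen by univariate screening.
- A bootstrap comparison of mean costs and QALYs between arms.

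None of these is a between-arm analysis of PAP hours. None of the between-arm comparisons mentions a covariate.

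**The severity data.** Under Eligibility in the Protocol, every qualifying route needs an HSAT result. The recruitment rows of the Data Collection table list "RDI, Mean O2 saturation, mean O2 saturation, time under 90" (per cent) from the HSAT. The Randomization section has the research associate assign arms through a website and describes no stratification. ESS, short SAQLI and HUI are completed at the baseline visit, which is booked after the arm is known.

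**The concern.** The trial's main claim will rest on one confidence limit for a difference in PAP hours, and the SAP does not say how that limit is obtained. The paired t tests cannot supply it. They compare patients with themselves, and patients untreated at entry have no baseline PAP hours. The logistic model works on a dichotomised outcome, while the margin is in hours.

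That leaves three things open. The choice between an adjusted and an unadjusted estimate could be made after the data are seen, in a trial where patients and providers know the arm. Any precision that baseline severity could add goes unused. And if the arms happen to differ in severity, and severity is related to PAP use, no planned analysis takes account of it.

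**Working it through.** **Inputs.** From the SAP's Sample Size section: margin 1 h, SD 2 h, power 90%, type I error 0.05, 69 per arm, 150 patients with three-month data. Assumed here: an equal split of the 150 (75 per arm), a true difference of zero for power, and R-squared for log RDI and mean saturation against PAP hours. The documents give no R-squared, so a range is shown.

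**1. Reproduce the plan's figure.** n per arm = 2 × SD² × (z₁₋α + z₁₋β)² / margin².
- One-sided 0.05: 2 × 4 × (1.645 + 1.282)² / 1 = 68.5, so 69 per arm and 138 in total. This matches the SAP.
- One-sided 0.025: 2 × 4 × (1.960 + 1.282)² / 1 = 84.1, so 85 per arm and 170 in total. This does not match.

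The plan therefore used one-sided 0.05 and the raw SD, with no allowance for covariates.

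**2. Precision and power with 75 per arm.** Residual SD = 2 × √(1 − R²) and SE = residual SD × √(2/75). Power is from the noncentral t distribution with noncentrality 1/SE. Using 146 degrees of freedom instead of 148 changes power by no more than about 0.01 percentage point. Equivalent extra patients = 150/(1 − R²) − 150.

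| Assumed R² | SE (h) | Cut in SE | Power, one-sided 0.05 | Power, one-sided 0.025 | Equivalent extra patients |
|---|---|---|---|---|---|
| 0 (unadjusted) | 0.327 | – | 92.0% | 86.0% | – |
| 0.02 | 0.323 | 1.0% | 92.4% | 86.7% | 3 |
| 0.05 | 0.318 | 2.5% | 93.1% | 87.7% | 8 |
| 0.10 | 0.310 | 5.1% | 94.2% | 89.4% | 17 |
| 0.20 | 0.292 | 10.6% | 96.1% | 92.5% | 38 |

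The last row is an upper case with no support in the documents. Entry mostly on RDI > 30 narrows the spread of severity, which would tend to lower R-squared.

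**3. Chance imbalance.** The standardised difference in a covariate between two arms of 75 has SD √(2/75) = 0.163, so its 95% limits are ±0.32. An imbalance at a limit shifts the unadjusted difference by √R² × 2 × 0.32, which is 0.09, 0.14 and 0.20 h at R² = 0.02, 0.05 and 0.10, against a margin of 1 h.

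Suppose the true difference is exactly -1 h. Given an imbalance at the limit, the chance of a false non-inferiority claim from the unadjusted comparison is 1 − Φ[(1.645 × 0.327 − shift) / (0.327 × √(1 − R²))]. The sign of the shift is reversed when the imbalance goes the other way.

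| Assumed R² | Imbalance favours ACP arm | Same imbalance against ACP arm |
|---|---|---|
| 0.02 | 8.4% | 2.6% |
| 0.05 | 10.8% | 1.6% |
| 0.10 | 14.0% | 0.9% |

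These are conditional rates at one extreme. About 2.5% of randomisations reach or exceed that limit in a given direction. Averaged over all randomisations the unadjusted rate is 5%.

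**The case against.** A reader might infer from the t-test sentence that the SAP fixes an unadjusted t test for the non-inferiority comparison. It does not: the sentence covers time to treatment initiation and patient demand. Nor is that t test the only between-arm comparison, since costs and QALYs are compared by bootstrap.

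A reader might also take the 8.4–14.0% figures as an inflated error rate. They are not. The standard error of an unadjusted comparison already allows for chance imbalance, and randomisation itself is the protection on average. The conditional rates show only what adjustment would remove if such an imbalance occurred.

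The strongest case for leaving the plan alone is that the gain may be negligible. Nothing in either document says that RDI or saturation predicts hours of PAP use. The SAP's search for predictors does not name them. At one-sided 0.05, power at 150 patients already exceeds the planned 90%. This stands, and it limits the point to a refinement. It does not supply the missing primary analysis, and it gives no reason to leave the choice of model open.

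Comparability of the saturation covariate is also a fair objection. Some referred patients are on oxygen, and under the Protocol's Triaging Process the lead sleep physician decides case by case whether a further HSAT without oxygen is needed. Mean saturation may therefore not mean the same thing in every patient, which is why oxygen status during the test should be recorded.

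**Conclusion.** The point holds as a low-cost improvement and does not show an error in the planned sample size or test validity. No between-arm analysis of three-month PAP hours is specified, and no covariate-adjusted arm comparison is pre-specified for any outcome, although HSAT severity is known before randomisation and no stratification is described.

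If R-squared is 0.02 to 0.10, adjustment with 75 per arm at one-sided 0.05 raises power by 0.4 to 2.2 percentage points, from 92.0% to 92.4–94.2%. At one-sided 0.025 the corresponding figures are 86.0% and 86.7–89.4%, so alpha needs to be stated as well. The sizes depend on the assumed R-squared, the SAP's SD of 2 h and an equal split of 150 patients.

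The other two benefits are protection given that a severity imbalance has occurred, and a model fixed before the data are seen. A reader might infer that the trial is underpowered or that an unadjusted comparison would be invalid. The documents support neither: 138 reproduces at one-sided 0.05, and an unadjusted comparison keeps its overall 5% error.

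**What to change.** Add to the SAP's Statistical Analysis section, in words such as these: *The between-arm difference (ACP minus physician) in mean nightly PAP hours at three months will be estimated by linear regression on arm, with RDI (log scale) and mean nocturnal oxygen saturation from the eligibility HSAT as covariates fixed in advance. Non-inferiority is concluded if the lower confidence limit, at a stated one-sided alpha, lies above -1 h. The unadjusted difference will be reported alongside.*

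Three details belong with it:
- State the one-sided alpha. The planned 138 corresponds to 0.05.
- Record whether the eligibility HSAT was done on oxygen.
- Do not adjust for ESS, SAQLI or HUI from the baseline visit, because they are collected after randomisation.

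The cost is a short SAP addition, a note of oxygen status during the HSAT, and two degrees of freedom out of 148.

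### The secondary predictor models dichotomise outcomes and screen covariates univariately with no correction for selection; the powered non-inferiority comparison is not affected

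*SAP*

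**What the plan says.** The Statistical Analysis section of the SAP gives the predictor models two sentences. The first sets their purpose and method, "Multiple logistic regression will be used to identify predictors of study outcomes", with covariates chosen "using variables identified as predictive on univariate regression". The second follows at once: "Outcomes will be transformed into binary variables based on clinically relevant cut-offs".

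Neither document names the cut-offs, the outcomes to be cut, the candidate variables, the screening threshold, or any shrinkage or internal validation. Resampling appears only in the economic analysis: "Using bootstrapping, we will compare the difference in mean costs and QALYs between the study arms".

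Elsewhere the SAP keeps outcomes on their measured scale. Change in clinical outcomes is analysed by t test ("Paired t tests will be used to compare clinical outcomes from baseline to 3 months and one year"), and so are time to treatment and patient demand. The Sample Size section works in hours: "A non-inferiority margin of -1 hour of PAP adherence was determined by consensus of the investigators", with "a standard deviation of 2 hours of nightly CPAP use".

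**The concern.** Two separate features weaken the predictor analysis.

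- **Splitting the outcome.** Nightly hours of use and questionnaire scores carry graded information. A binary version treats everyone on the same side of the cut as identical. With about 150 patients, that can decide whether a moderate predictor is detected.
- **Screening on the same data.** A variable enters the multiple model because its estimate happened to look strong in these patients. The final odds ratios, p values and discrimination are then computed from those patients as if the model had been fixed beforehand. Estimates that pass the screen are too large on average, and the reported uncertainty ignores the selection.

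At stake is the reliability of any published list of predictors of adherence or symptom response. Real predictors may be missed, and chance ones may be reported with too much confidence.

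**Working it through.** **1. The plan's own figure.** The documents give no figure for the predictor models. The sample size can be reproduced: margin 1 hour, SD 2 hours, true difference 0, "90% power with a type I error of 0.05" (taken as one-sided).

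n per arm = 2 × SD² × (1.645 + 1.282)² / margin² = 2 × 4 × 8.56 / 1 = 68.5, rounded up to 69, so 138 in total. This matches the SAP and uses continuous hours throughout, so the dichotomisation plays no part in it.

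**2. Information lost by a binary split, if the outcome is normal.** With p the proportion below the cut, z_p the matching normal quantile and φ the normal density, relative efficiency = φ(z_p)² / [p(1 − p)]. N = 150 is the SAP's target for patients with three-month adherence data.

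| Split | Relative efficiency | Loss | 150 patients inform like |
|---|---|---|---|
| 50/50 | 0.3989² / 0.25 = 0.637 | 36.3% | 95.5 |
| 25/75 | 0.3178² / 0.1875 = 0.539 | 46.1% | 80.8 |
| 20/80 | 0.2800² / 0.16 = 0.490 | 51.0% | 73.5 |

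The median cut is the best case. Making up its loss would take 150 / 0.637, or about 236 patients.

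**3. The same loss as power.** Simulation with N = 150, one normal predictor, two-sided 0.05 and 1,500 runs per setting:

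| Correlation | Linear | Logistic, median cut | Logistic, 30/70 cut |
|---|---|---|---|
| 0.20 | 70% | 50% | 45% |
| 0.25 | 88% | 69% | 63% |
| 0.30 | 96% | 85% | 80% |

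**4. Where the loss disappears.** Assume that adherence falls in two clusters: 40% of patients around 2 hours and 60% around 6 hours, with SD 0.9 within each. Let the predictor act on which cluster a patient belongs to, and cut at 4 hours. Logistic regression then had power of 61% against 56% for linear, and 80% against 73% for a stronger predictor. Nothing was lost. This depends on how the predictor acts. If it shifts everyone's hours by the same amount in that distribution, the efficiency of the 4-hour cut is only 0.03.

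**5. Screening with nothing to find.** N = 150, 40% event rate, independent pure-noise candidates, 200 runs per setting. AUC is the mean apparent value among runs that selected any variable; the true value is 0.50.

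| Candidates | p<0.05: runs selecting any | p<0.05: AUC | p<0.20: runs selecting any | p<0.20: AUC |
|---|---|---|---|---|
| 10 | 34% | 0.62 | 90% | 0.62 |
| 20 | 62% | 0.63 | 100% | 0.66 |
| 30 | 78% | 0.65 | 100% | 0.70 |

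**6. Screening with one real predictor.** N = 150, about 40% events, 1,000 runs per setting. The last column is the mean log odds ratio among runs where the predictor passed, divided by its true value.

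| True OR per SD | Threshold | Passed | Inflation |
|---|---|---|---|
| 1.3 | 0.05 | 33% | 1.77 |
| 1.3 | 0.20 | 63% | 1.41 |
| 1.5 | 0.05 | 63% | 1.26 |
| 1.5 | 0.20 | 87% | 1.13 |

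Step 6 isolates the effect of selection. The AUC in step 5 also contains ordinary overfitting, which a full unscreened model shares. The fix therefore needs optimism correction as well as the removal of screening.

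The candidate counts, thresholds, event rate and independence in steps 5 and 6 are assumptions, because the SAP gives none. For scale, the summary sheet in Appendix 1 of the Protocol lists 15 comorbidities, and baseline scores, sleep-test measures and medications are collected too.

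**The case against.** The strongest reply is that these models are secondary. The trial is powered on hours, its t tests keep the measured scale, and QALYs use mean utilities. A clinically meaningful threshold is easy to interpret, and if adherence really is two clusters a split may cost nothing. All of this stands, and it limits the point to the predictor models. It does not answer the screening problem, which is present whatever the distribution. A clinical cut-off also protects against a data-driven choice only if it is named beforehand, and none is.

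Three stronger readings are tempting, and the documents do not support them.

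- A reader might infer that more than a third of the information is always lost. That needs a roughly normal outcome. The documents give neither outcome distributions nor cut-offs, and step 4 shows an exception.
- A reader might take the 15 comorbidities and calculate 1 − 0.95^15 = 54% as the harm done by screening. That figure is the chance of at least one p<0.05 among 15 independent null tests. Testing all 15 in one fixed model would give much the same, so it measures multiplicity. The listed conditions also plainly overlap (kidney disease and dialysis, for example), and the SAP gives no threshold.
- A reader might treat predictor-finding as a trial objective, or fear that screening drops confounders of the arm comparison. The SAP mentions predictors only as the purpose of one method. Arm is randomised, and these models are not described as estimating its adjusted effect.

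**Conclusion.** The point holds for the secondary predictor models only. Following the SAP as written gives a weaker and more optimistic analysis than the same data allow, so this is more than a missing detail.

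Under approximate normality the split loses about 36% of the information at best and about half at a 20/80 cut. For a clustered outcome the loss can be smaller or nil. Uncorrected screening inflated the log odds ratio of a selected real predictor by 1.13 to 1.77 times in the settings tried, and gave noise models the appearance of discrimination. These sizes rest on the stated assumptions. The direction was the same at every threshold and candidate count examined.

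Chance predictors may be reported and real ones missed; the documents do not allow a firmer statement than that. The change is a cheap improvement and does not bear on the validity of the main comparison.

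**What to change.** Amend the predictor paragraph of the SAP, before outcome data are examined, as follows.

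1. For each outcome recorded on a continuous scale, make linear regression the main predictor model.
2. Include arm and a candidate list of baseline variables fixed in advance. The list should be broad enough to serve the aim of finding predictors, including the comorbidities of interest, with overlapping conditions grouped so that its length suits about 150 patients.
3. Drop univariate screening. State in advance whether the full pre-listed model or a penalised model will be used.
4. Report bootstrap optimism-corrected performance, repeating any penalty tuning in every resample.
5. Name each clinical cut-off now. Use it for a descriptive proportion by arm or a supporting logistic model, which also covers the case of clustered adherence.

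The cost is SAP wording and slightly more analysis work. Coefficients will be in hours or points rather than odds ratios. No extra patients, visits or data are needed.

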For patients assigned to the “Fast Track” arm, the Fast Track clinic supervisor will schedule an appointment for the patient with an ACP. For patients assigned to the standard treatment arm, the booking clerk will schedule an appointment for the patient with a sleep physician. Patients will be asked to arrive 15 - 20 minutes prior to the appointment to complete study questionnaires. The booking clerks will notify the RA of the initial appointment date and time.

STUDY PROCEDURE

BASELINE VISIT & TREATMENT PLAN

When patient arrives, the RA will ask the patients to complete the following questionnaires (ESS, Short SAQLI without treatment section, and HUI). The study will require an ESS at the time of the baseline visit, even though there may be multiple ESS questionnaires in the patient's chart.

If required, the sleep physician will order a polysomnography (PSG). The RA will check that the PSG is ordered as "urgent". The following will be collected: PSG date, AHI, mean oxygen saturation and percentage of time under 90%.

The RA will access the CPAP database to retrieve the patient's treatment type. The RA will retrieve the patient's treatment start date for the following treatments by:

- CPAP/BAP – retrieving and calling the homecare company OR CPAP database,
- Oxygen only – looking at the patient's chart for the date when the patient was contacted about the PSG results (if the patient is previously on oxygen) OR determining when the patient started on oxygen,
- Dental appliance – calling the dentist,
- Weight loss – looking in the patient's chart for the date treatment options were offered

Possible scenarios	Action
Patient cancels or does not show to the appointment	The RA will note the original appointment date and the rescheduled date.
Patient does not show for 3 or more appointments	Patient is discharged from the CPAP clinic and the study.
Patient stops their initial treatment	The RA will note new treatment. 3-month and 1-year appointments will still be based on the original treatment date.
Multiple patients need to meet the RA at the same time (recruitment, clinical visits)	Possible options: 
 1) Ask an another RA to assist in one of the appointments 2) Ask The Fast Track clinic supervisor to obtain clinical study data at visit

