Patients with only a verbal consent to the study	The RA will review the study with the patient and obtain a written consent to the patient regardless if the patient is eligible or not. 
If the patient revokes their verbal consent, the RA will remove patient from the study, identify the reason why the patient does not want to participate in the study. Because the patient has not yet had an initial appointment with a physician or an ACP, the patient will not be counted as part of the 150 patients recruited.
 
The RA will notify the Fast Track clinic supervisor of patient.

Patient delays their treatment	If the patient delays their treatment due to insurance purposes, treatment start date will be the date they start their treatment. 
If the patient delays their treatment due to other medical reasons, the treatment start date will be the date that treatment was offered. Three-month and one year follow-up data will be collected as per usual procedures.

Patient has had multiple PSGs after the indicated treatment start date	The RA will pull the file and review with the LSP as the treatment start date may need to be modified.
Patient does not have sleep disordered breathing after further testing (e.g., PSG)	The treatment start date will be the date of the diagnostic test. Three-month and one year follow-up data will be collected as per usual procedures.

3-MONTH & 1-YEAR FOLLOW-UP (\pm 2 WEEKS)

3-Month Appointment Date and Time

The RA will create a list (weekly) of patients who have completed their initial appointment for the booking clerk. The booking clerk will review the scheduling system to book and/or confirm patient's 3-month appointment. Upon receiving the appointment date, the RA will complete a HSAT requisition for the booking clerk to book patient for a HSAT (in-house or with the patient's CPAP company – if ordering a HSAT from the home care provider, state on cover letter to send the raw data to FMC Sleep Centre) on the day of the follow-up appointment or whenever is most convenient for the patient. HSAT test is to be completed with a Remmers recorder. Note: if the patient is on O2, request the HSAT done on room air or without O2. If the HSAT is completed on O2 note make a note that it was completed on O2 on the patients chart.

1-Year Appointment Date and Time

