The RA will create a list (every 3 months) of patients who have completed their 3-month follow-up appointment for the booking clerk. The booking clerk will create a tracking task in the scheduling system to book the appointment several months before the 1-year target date. When the appointment is book, booking clerk will notify RA of appointment date and time. Upon receiving the appointment date, RA will complete a HSAT requisition for the booking clerk to book patient for a HSAT (in-house or with the patient's CPAP company) on the day of the follow-up appointment or whenever is most convenient for the patient. HSAT test is to be completed with a Remmers recorder.

The RA will attempt to call all three month and one year patients who do not have a follow up appointment booked through the Sleep Centre to coordinate the best date and time to complete the questionnaires.

If the patient does not have a follow-up appointment booked at the Sleep Centre. We will use the date that the patient returns their questionnaire as the final appointment date; however, the research associate should note that it is the follow-up date not the final appointment date.

At Time of Appointment

The RA will give the patient a questionnaire package (ESS, Short SAQLI including treatment section, HUI, VSQ-9) at the time of visit. The ESS, Short SAQLI including treatment section and the HUI surveys are to be completed before the patient enters the clinical appointment. The VSQ9 survey is

to be completed after the patient completes their clinical appointment. Download data will be obtained by the Fast Track clinic supervisor or by the therapist. The patient will not be compensated for parking if the follow-up visit is part of the patient's clinical care.

If there are any information missing from the Fast Track Summary sheet (i.e. Triaging criteria, co-morbidities or medication), the RA will retrieve them from the chart or from the CPAP database before/during the time of visit.

Possible scenarios	Action

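### The SAP names no baseline-HUI adjustment for the incremental QALY, which costs precision and leaves part of any baseline gap in the estimate

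*SAP*

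**What the plan says.** The QALY method is in the economic paragraph of the SAP, Statistical Analysis. Utilities come first: "An estimate of mean utility scores based on the HUI questionnaire will be calculated". An average QALY per arm follows, and then the comparison: "Using bootstrapping, we will compare the difference in mean costs and QALYs between the study arms". No covariate, regression or QALY formula is given. The economic sensitivity analyses are about prices: "Sensitivity analyses will be performed to evaluate the effect of changes in physician fees, RT salaries, diagnostic testing costs and treatment costs". None concerns utilities. The only regression in the SAP is logistic, for predictors of outcomes cut into binary variables; it does not estimate the QALY difference.

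The data for an adjustment exist. In the Protocol, Baseline Visit & Treatment Plan, "the RA will ask the patients to complete the following questionnaires (ESS, Short SAQLI without treatment section, and HUI". Under "3-MONTH & 1-YEAR FOLLOW-UP" HUI is collected again: "The RA will give the patient a questionnaire package (ESS, Short SAQLI including treatment section, HUI, VSQ-9) at the time of visit".

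Three features of the Protocol affect how the baseline value can be used. Randomisation comes before the baseline visit is booked. The note that closes Consenting Process says that appointment availability depends on the assigned arm. The 3-month and 1-year appointments are dated from treatment start, not from the baseline visit.

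**The concern.** Baseline HUI is normally one ingredient of a one-year QALY and also predicts the later HUI values that make up the rest. If one arm starts with higher utility, its mean QALY will tend to be higher whatever the care model does. A comparison of arm means leaves that carry-over in the point estimate. It also leaves in the QALY variance the part that baseline HUI explains.

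This matters because two ways of delivering the same therapy may differ little in QALYs. The sample size calculation itself reproduces with a true adherence difference of zero. The incremental QALY is the denominator of the ICER, so avoidable noise in it passes straight into the cost-effectiveness result.

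**Working it through.** **The plan's own figure.** The documents give no figure for HUI, QALYs or the ICER. The one sample size, for PAP adherence, reproduces: n per arm = 2(1.645 + 1.282)² × 2² / 1² = 68.5, rounded up to 69, or 138 in total (one-sided 0.05, 90% power, true difference zero). It is not in dispute here.

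**Inputs**
- 75 per arm: the SAP's 150 patients with three-month adherence data, assumed to split equally.
- HUI at 0, 3 and 12 months (Protocol), treated for this check as measured from a single origin.
- QALY taken as the trapezoidal area under HUI (assumption; the SAP gives no formula). Weights: 0.25/2 = 0.125 at baseline, (0.25 + 0.75)/2 = 0.5 at 3 months, 0.75/2 = 0.375 at 12 months.
- HUI SD of 0.15 to 0.30, equal at all visits, and one common correlation ρ of 0.3 to 0.8 (assumptions; the documents give neither).

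**Formulae**
- Share of a baseline gap carried into the QALY difference: b = 0.125 + 0.875ρ.
- QALY variance in units of SD²: v = ρ + (1 − ρ)(0.125² + 0.5² + 0.375²) = ρ + 0.40625(1 − ρ).
- Variance left after adjustment: v − b². Proportional cut: b²/v.
- SE of the baseline HUI difference: SD × √(2/75) = 0.1633 × SD.

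**Results at SD 0.20** (SE of the baseline difference 0.0327)

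| ρ | b | QALY shift from a one-SE baseline gap | SE unadjusted | SE adjusted | Variance cut |
|---|---|---|---|---|---|
| 0.3 | 0.39 | 0.013 | 0.025 | 0.022 | 26% |
| 0.5 | 0.56 | 0.018 | 0.027 | 0.020 | 45% |
| 0.6 | 0.65 | 0.021 | 0.029 | 0.019 | 55% |
| 0.7 | 0.74 | 0.024 | 0.030 | 0.017 | 66% |
| 0.8 | 0.83 | 0.027 | 0.031 | 0.015 | 77% |

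Example, ρ = 0.5: v = 0.5 + 0.40625 × 0.5 = 0.703; b² = 0.5625² = 0.316; cut = 0.316/0.703 = 45%.

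Shifts and SEs scale with the SD. Over SD 0.15 to 0.30 and ρ 0.3 to 0.8, the one-SE shift runs from 0.0245 × 0.3875 = 0.009 to 0.0490 × 0.825 = 0.040 QALY. The percentage cuts do not depend on the SD or, to a close approximation, on the number analysed.

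**Fewer patients at 1 year.** Applying the SAP's 15% loss to 75 as an illustration leaves about 64 per arm, and every SE grows by √(75/64) = 1.08.

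**Simulation.** In 20,000 simulated trials with no true difference (SD 0.25, ρ 0.5, 75 per arm), the estimate moved with the baseline gap at a slope of 0.56 unadjusted and about 0.00 adjusted. The SE was 0.034 unadjusted and 0.026 adjusted. Both estimators averaged about zero.

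**The case against.** **Randomisation already makes the difference unbiased.** This stands. Both estimators averaged zero in simulation, and a bootstrap interval for the unadjusted difference already reflects chance imbalance. A reader might infer that the planned comparison is biased; under randomisation it is not. What remains is lost precision, and a point estimate that is off in whichever trial happens to have a baseline gap. The carry-over is also partial, not one for one.

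**The SAP does not say that the difference is unadjusted.** True: it is silent on both the formula and adjustment. The plain reading of a difference in means is unadjusted, but the defect is the silence. If baseline HUI were left out of the QALY, a gap would still enter through the correlation.

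**Adjustment would not settle the ICER.** Also true. One might infer that a baseline gap will reverse the ICER's sign and that adjustment would prevent this. The documents give no expected QALY difference, so that cannot be claimed. At SD 0.20 and ρ = 0.6, with an assumed true difference of 0.01 QALY, the chance of a wrong-signed estimate falls only from about 36% to 30%; at 0.02 it falls from about 24% to 15%. A small true difference leaves the ratio unstable either way.

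**The baseline value is not a clean covariate.** This is the most serious objection, and part of it stands. HUI is completed before the first consultation but after randomisation, at a visit whose timing can depend on arm. A gap may therefore not be purely chance, and adjusting could absorb a real utility effect of waiting. Using a pre-randomisation HUI instead is not an option, because none is collected. If the modified intention-to-treat set applies here, selecting on three-month adherence data may create further imbalance that adjustment only partly addresses. These are reasons to report both results and state the limitation.

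**The time axis is approximate.** Follow-up is dated from treatment start, so the 0, 3 and 12 month weights are a simplification, and the time between baseline visit and treatment start has no stated place in the QALY.

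**Conclusion.** The point holds as one of precision and specification. The SAP names no adjustment for baseline HUI and no QALY formula, although the data for both are collected. An unadjusted difference would carry about 0.39 to 0.83 of any realised baseline gap, and adjustment would cut its variance by about 26% to 77%, for correlations of 0.3 to 0.8.

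These sizes rest on the trapezoidal QALY, equal SDs and a common correlation. The absolute figures also rest on the assumed SD and on 75 per arm, which counts patients with three-month adherence data and may exceed the number with 1-year HUI. The documents do not support a claim of average bias or of a predicted ICER sign change. The non-inferiority comparison of adherence, on which the trial is powered, is unaffected.

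**What to change.** In the economic paragraph of the SAP:

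1. Define each patient's QALY as the area under HUI, using actual assessment dates and a stated time origin, and say how the interval between baseline visit and treatment start is counted.
2. Bootstrap patients, keeping each patient's cost and QALY together. In each resample, estimate the incremental QALY by regression on arm and baseline-visit HUI.
3. Report the unadjusted difference as a sensitivity analysis.
4. State the limits: baseline HUI is taken after randomisation at an arm-dependent time, so adjustment may absorb an effect of waiting, and it only partly addresses imbalance created by the modified intention-to-treat set.

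The cost is a few sentences in the SAP and a little programming. No new patients or questionnaires are needed. The one methodological downside is the possible absorption of a waiting effect, which is why the unadjusted result should stay in the report.
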